- C. Explain whether the biospecimens will be shared with other investigators, inside and outside of JHU, how the decision to share will be made, and by whom. Include your plans, if any, for commercial use. Also explain how downstream use of the specimen will be managed, and what will happen to left-over specimens.

- D. Describe whether future research using the biospecimens will include specimen derivation and processing (cell lines, DNA/RNA, etc.), genomic analyses, or any other work which could increase risk to participants. Explain what additional protections will be provided to participants.

- E. If future research could yield unanticipated incidental findings (e.g., an unexpected finding with potential health importance that is not one of the aims of the study) for a participant, do you intend to disclose those findings to the study participant? Please explain your position.
- F. Explain whether the specimens will be identifiable, and if so, how they will be coded, who will have access to the code, and whether the biospecimens will be shared in linked (identifiable) form.
- G. Explain whether the repository will have Certificate of Confidentiality protections.
- H. Explain whether a participant will be able to withdraw consent to use a biospecimen, and how the repository will handle a consent withdrawal request.
- I. Describe data and/or specimen use agreements that will be required of users. Provide a copy of any usage agreement that you plan to execute with investigators who obtain biospecimens from you.

XIV. Data Coordinating Center:

Complete if JHSPH serves as the Data Coordinating Center.

- A. How will the study procedures be developed?
- B. How will the study documents that require IRB approval at each local site be developed? Will there be some sort of steering or equivalent committee that will provide central review and approval of study documents, or will template consent forms, recruitment materials, data collection forms, etc. be developed by and provided to the local sites by the coordinating center without external review?
- C. Will each local clinical site be overseen by its own IRB with an FWA, or will a Single IRB review the study? State whether the coordinating center will collect IRB approvals and renewals from the clinical centers; if not, explain why.
- D. How will the coordinating center provide each local site with the most recent version of the protocol and other study documents? What will be the process for requesting that these updates be approved by local clinical center IRBs?

E. What is the plan for collecting data, managing the data, and protecting the data at the coordinating center?

F. What is the process for reporting and evaluating protocol events and deviations from the local sites? Who has overall responsibility for overseeing subject safety: the investigators at the recruitment site, the Coordinating Center, the Steering Committee, or a Data and Safety Monitoring Board (DSMB)? Is there a DSMB that will evaluate these reports and provide summaries of safety information to all the reviewing IRBs, including the coordinating center IRB? Please note that if there is a DSMB for the overall study, then the coordinating center PI does not have to report to the coordinating center IRB each individual adverse event/problem event that is submitted by the local site PIs.

G. Some FDA regulated studies have different AE reporting criteria than that required by the IRB (IRB Policy No. 103.06). How will you reconcile the different requirements, and who is responsible for this reconciliation?

H. Who is responsible for compliance with the study protocol and procedures and how will the compliance of the local sites be monitored and reviewed? How will issues with compliance be remedied?

XV. Drug Products, Vitamins, Food and Dietary Supplements:

Complete this section if your study involves a drug, botanical, food, dietary supplement or other product that will be applied, inhaled, ingested or otherwise absorbed by the study participants. If you will be administering drugs, please upload the product information.

A. List the name(s) of the study product(s), and the manufacturer/source of each product.

Name of Study Product	Manufacturer/Source

B. List each study product by name and indicate its approved/not approved status.

Approved by the FDA and Commercially Available	Approved by Another Gov't Entity (provide name)	Cleared for Use at Local Study Site

- C. If your study product has an Investigational New Drug (IND) application through the U.S. Food and Drug Administration, provide the IND number, and the Investigators Brochure.
- D. If your study product is a marketed drug, provide the package inserts or other product information. If the study product WILL NOT be used for its approved indication, dose, population, and route of administration, provide a detailed rationale justifying the off-label use of the study product.
- E. If the study product does not require FDA approval (e.g., dietary supplements, botanicals, products not subject to the U.S. FDA, etc.), provide safety information (as applicable) and a certificate of analysis.
- F. Explain who will be responsible for drug management and supply, labeling, dispensing, documentation and recordkeeping. Complete and upload into PHIRST the Drug Data Sheet available on the JHSPH IRB website at www.jhsph.edu/irb.
- G. What drug monitoring and/or regulatory oversight will be provided as part of the study?

XVI. Medical Devices:

Complete this section if your study will involve an approved or investigational medical device (**diagnostic**, non-significant risk, significant risk).

- A. List the name(s) of the study product(s), the manufacturer/source of each product, and whether or not it is powered (electric, battery). Provide product information. If it is electric, upload documentation of clinical engineering approval or its equivalent from a local authority, to ensure that the device is in good working order.

Name of Study Product	Manufacturer/Source	Powered?
Oraquick Advance HIV rapid test	Orasure Technologies	No
FLOQ Swabs	Copan flock technologies	No

- B. List each study product by name and indicate its status as approved by a government authority or not approved.

Approved by the FDA and Commercially Available	Approved by Another Gov't Entity (provide name and approval information)	Not Approved
Oraquick Advance HIV rapid		

test		
FLOQ Swabs		

C. If your investigational device is Exempt from the FDA IDE regulations, explain which section of the code applies to your device and why it meets the criteria provided. If it is a **diagnostic device**, provide pre-clinical information about the sensitivity and specificity of the test and the anticipated failure rate. If you plan to provide the results to participants or their physicians, justify doing so, and explain how those results will validated (or not) against the current “gold standard”.

N/A

D. If you believe the investigational device is not IDE exempt under 21CFR 812.2(c), but is a “Non-Significant Risk” device considered to have an approved IDE application, provide information from the manufacturer supporting that position.

N/A

E. If you are using an investigational device that is a Significant Risk Device, provide the IDE number given by the FDA, or if not under FDA jurisdiction, explain why it is appropriate to use this device in this study. Provide a description of the device, and upload a picture or manufacturing schematics into PHIRST. Provide any other information relevant to a determination of its safety to be used for the purposes outlined in this research plan.

N/A

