Session 1: Participants will be asked to view the home-based testing website using their smart phones (if applicable) or on a provided study computer. They will be asked to navigate the website, establish an account, and go through the steps for requesting kits. These participants will also be asked to give their opinion on the design and content of cards that will be used to refer their peers and sex partners to the study and the website. Then we will ask participants to take time over the following week to talk to their peers and/or sex partners about the website and show them these coupons so that they too can view the materials and provide comments.

Session 2: Participants will be asked to share how the conversations went with peers/sex partners, including any challenges they experienced, acceptability of the coupon design and suggestions to improve the program.

Both sessions will be audio recorded to allow researchers to listen to the discussions. The recordings will be kept on a secure computer with limited access.

Full Trial: See Star Participant Flow for an overview

Index: All Index procedures are being conducted fully remotely via phone calls.

[Baseline Visit] The participant will be contacted by the research assistant via phone at a time that was scheduled based upon the participant's convenience. Informed consent/assent will be obtained and a copy will be emailed to the study participant. The participant will be given the choice of completing the survey self-administered or by the research assistant. If the participant chooses self-administered a link to the Qualtrics survey will be emailed. If the participant chooses research assistant administered the research assistant will directly input responses into the Qualtrics link. No names will appear on the survey data - only a unique code. After the survey, locating information will be collected. This information will be stored in an encrypted and password protected database that is separate from the survey data and the unique code. The participant will be provided with the date and time of the first group session. The participant will receive \$50 for completing the baseline visit.

[Randomization] Index Participants will be randomized after the baseline survey and scheduled for their first session with the Health Educator. All Index participants are eligible to be randomized up to 60 days after they complete their baseline visit.

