[Experimental condition]: Peer Mentor Training is 5 individual sessions with a 30 day check-in session. This condition is focused on training Index with communication skills to promote HIV and STI testing and treatment and pre-exposure prophalaxis (PrEP) to individuals in their social networks. Peer Mentor training is conducted by a one health educator. The sessions are held once a week and will last approximately 60 minutes. The attached table outlines each session, objectives and main activities. Participants will receive \$25 for each session they attend.

[Control condition]: Is one individual-based session which will be conducted by sending a video of a health educator. The session is designed to last up to 60 minutes. The content of the session will include an overview about chlamydia, gonnorhea and HIV, home-based testing and specimen collection procedures and the Star website. At the end of the session participants will be given six invitations labeled with Starcodes and instructed to use them to invite friends, peers or sex partners from their social network to enroll into the study and access free home-based testing kits. Participants will receive \$25 for attending this session.

[Home-based testing and specimen collection kits]: All randomized Index and the networks that they invite and to the study will have access to a secure encrypted website that will enable them to request kits to test for HIV at home and collect specimens that can be mailed to a laboratory for testing for gonorhea and chlamydia. The following are the steps a participant will follow when using the website:

- You will set up a personal account on the study website that will have a user name and password that you choose. By logging into your account you will be able to view the kits you requested, the dates they were mailed to you, the results to gonorhea and chlamydia testing and to enter the results of your HIV home-based test.
- After you set up the account you will be able to view information about the different sexually transmitted infections and treatment and other resources.
- The kits will be mailed to you within 3-5 business days in a plain white envelope to the address that you want. The envelope will not indicate anything about the contents or reference the study.
- Instructions will be included in the envelope on how to use the different test kits.

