- For the HIV testing – you will collect an oral swab at your home, place it in a vial of solution and will read your result in 20 minutes.
- For gonorrhea and chlamydia testing you will place the specimens in a plastic tube that we provide and mail to the lab for testing. Postage for this will be paid by the study. These specimens will only be labeled with a unique ID number and not your name. The laboratory will

dispose of the swabs after the testing is complete. The results of these tests will be available to view in your website account within one week of the lab receiving your specimens. Your test results will be communicated to you via your account on the STAR project website

Maryland State names reporting: This is a requirement for gonorrhea and chlamydia tests. Participants who request these kits are required to read and acknowledge the Maryland State names reporting (see website mock up). The HIV test result is not required to be reported to the State.

[3 month follow-up visit]: Three months from the date of the last group session, Index participants will be contacted to schedule their in-person follow-up visit. Networks will be sent an email with a message reminding them that it is time for their 3 month follow-up survey via the STAR website.

2. Describe the number and type of study visits and/or contacts between the study team and the participant, how long they will last, and where/how they will take place.

Component testing: Participants will take part in two group-based sessions on site at the Lighthouse. These will be scheduled one week apart. Each session could last up to two hours.

Full trial:

Index:

Baseline visit: up to 60 minutes - over phone or self-administered

Intervention group sessions (five) and check-in session if applicable: up to 90 minutes - private group room at the Lighthouse Studies @ Peer Point

3 month follow-up visit: up to 60 minutes - private office in the Lighthouse Studies @ Peer Point

Network:

Enrollment visit: up to 45 minutes, online www.star.jhsph.edu

3 month follow-up visits: up to 45 minutes, online www.star.jhsph.edu

3. Describe the expected duration of the study from the perspective of the individual participant and duration overall.

Component testing: Each session could last up to two hours. Therefore the duration of participation is up to four hours.

Full trial:

Index participant: The duration of the study is up to 4-6 months from screening to 3 month survey.

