Aim 2: We will compare the reach of the two conditions in terms of (i) the number of peers recruited to access the self-testing website; and (ii) the characteristics of those recruited including sexual risk behavior, HIV/STI testing behavior, linkage to HIV/STI care, PrEP awareness and self-testing-related perceived norms. For the first part, as the number of peers/sex partners recruited by a mentor is a count, we will fit a model with log link with intervention condition as the only predictor to estimate the treatment-to-control ratio of mean number of peers recruited. For the second part, as the peers are clustered in the mentors who recruited them, we will use general estimating equations (GEE, which allow correlation among clustered units) to estimate treatment-control contrasts in each characteristic. We will include sex as a biologic variable in these analyses.

Aim 3: We will test and estimate differences (i) between intervention and control mentors and (ii) between intervention and control recruited peers in terms of: request of self-testing kits, return of specimens for STI testing, accessing of STI test results, and posting of HIV oral test result (all binary variables). For the mentors, we will use tests of two sample proportions and simple logistic regression with the intervention condition as predictor. For the peers, we will fit GEE logistic models to allow for correlation of outcome among clustered peers and will include sex as a biologic variable.

Secondary Analysis

Changes in knowledge and self-efficacy: We will examine the changes in the continuous measure of Knowledge score using linear regression adjusting for baseline knowledge score and other covariates. We will examine changes in self-efficacy by using a Chi-square test for a difference between two proportions of efficacy score.

Reasons for testing and future preferences: We will tabulate participant responses and compare proportions by condition using Chi-square tests.

5. Answer the following if they are relevant to your study design:

A. If the study has different arms, explain the process for assigning participants (intervention/control, case/control), including the sequence and timing of the assignment.

Component Testing: N/A

Full Trial:

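### The Index follow-up runs from the last session, about 28 days later in the experimental arm, and no common counting window is stated for Index kit outcomes or peers recruited

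*Combined protocol and SAP*

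**What the plan says.** **Anchor.** Section V.C.1 sets the Index visit by the last session: "Three months from the date of the last group session, Index participants will be contacted to schedule their in-person follow-up visit".

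**Sessions.** The same section describes the control condition: "Is one individual-based session which will be conducted by sending a video of a health educator". For the experimental condition it says "Peer Mentor Training is 5 individual sessions with a 30 day check-in session", and "The sessions are held once a week and will last approximately 60 minutes".

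**Timeline.** Section V.C.3 states "Index participant: The duration of the study is up to 4-6 months from screening to 3 month survey". Section V.C.1 allows a wait before assignment: "All Index participants are eligible to be randomized up to 60 days after they complete their baseline visit". Section III.A names baseline and the 3-month follow-up as the only data collection points.

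**Analysis.** In Section V.C.4, Aim 2 counts peers recruited per Index: "we will fit a model with log link with intervention condition as the only predictor". Aim 3 compares four yes/no website outcomes: "request of self-testing kits, return of specimens for STI testing, accessing of STI test results, and posting of HIV oral test result". For Index men it uses two-proportion tests and logistic regression on condition alone. Neither aim says when counting starts or stops.

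**Access.** Section V.C.1 gives website access to all randomized Index men, with no opening or closing day. Section V.C.3 gives each network member three months from that member's own enrollment, in both arms.

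**The concern.** Timing follow-up from the last session gives both arms the same time after their intervention ends. It does not give them the same time since they started. For a survey measure such as knowledge this may be reasonable. For an outcome that accumulates, such as ever having requested a kit or the number of peers recruited, the arm observed longer will tend to score higher whatever the training does.

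The plan names no data collection point after the 3-month follow-up and ends Index participation at that survey. Closing each man's website record at his own visit is therefore the natural reading, although it is not stated. If that is done, part of any between-arm difference could come from extra days. Aim 3 exists to produce preliminary effect sizes on self-testing uptake, and those estimates would carry the excess.

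**Working it through.** **1. Visit day, counted from session 1** (three months = 91 days)

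- Control: last session on day 0, so 0 + 91 = day 91.
- Experimental, session 5 last: 4 weekly gaps × 7 = day 28, so 28 + 91 = day 119. The gap is 28 days and the ratio 119/91 = 1.31.
- Experimental, check-in last (taken as 30 days after session 5): 28 + 30 + 91 = day 149. The gap is 58 days and the ratio 149/91 = 1.64.

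**2. Check against the stated Index duration of up to 4-6 months** (30.44 days per month, 0 to 60 days from baseline to randomization, session 1 taken at randomization)

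- Session 5 anchor: 119/30.44 = 3.9 to (60 + 119)/30.44 = 5.9 months. This reproduces the stated range.
- Check-in anchor: 149/30.44 = 4.9 to 209/30.44 = 6.9 months. This overshoots at the longest wait but fits when the wait is 33 days or less.
- Control: 91/30.44 = 3.0 to 151/30.44 = 5.0 months.
- The maximum Index payment of $250 in Section IX.C equals 50 + 6 × 25 + 50, so the check-in may be a paid sixth session.

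Session 5 is the likelier anchor, but the check-in is not excluded. The direction of the gap is the same under both.

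**3. Index kit requests with no training effect** (assumptions: 40% control uptake by day 91, exposure from session 1 in both arms, counts closed at the visit, 70 per arm from 140/2 with equal allocation)

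Experimental uptake = 1 − 0.6^r, where r is the ratio of cumulative request hazard at day 119 to that at day 91. The last column is the exact rejection rate of a pooled two-proportion test at two-sided 5%. With equal uptake of 40% in both arms it is 4.9%.

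| Request pattern | r | Experimental uptake | Excess (points) | Test rejects |
|---|---|---|---|---|
| Rate halves every 14 days | 1.008 | 40.3% | 0.3 | 4.9% |
| Rate halves every 30 days | 1.066 | 42.0% | 2.0 | 5.5% |
| Weibull, shape 0.5 | (119/91)^0.5 = 1.144 | 44.2% | 4.2 | 7.9% |
| Constant rate | 119/91 = 1.308 | 48.7% | 8.7 | 18.0% |

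For the halving rows, r = (1 − 2^(−119/h)) / (1 − 2^(−91/h)), with h = 14 or 30. The constant-rate odds ratio is (0.487/0.513)/(0.4/0.6) = 1.43. At 20% and 60% control uptake, the constant-rate results are 1 − 0.8^1.308 = 25.3% and 1 − 0.4^1.308 = 69.8%.

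**4. Sensitivity to when experimental men can start** (constant rate)

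- Access from session 3 (day 14): 119 − 14 = 105 days, and 1 − 0.6^(105/91) = 44.5%.
- Access from session 5 (day 28): 91 days, 40%, no excess.
- If the check-in is the anchor and access starts at session 1: 1 − 0.6^(149/91) = 56.7%.

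**5. Peers recruited (Aim 2)**, with the six-invitation limit of Section III.B

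Take counts as negative binomial with shape 1 and pre-cap mean m. The capped mean is m(1 − q^6), with q = m/(1 + m). The experimental mean before the cap is m × 119/91 if invitations come at session 1.

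- m = 2: control 1.82, experimental 2.24, ratio 1.23.
- m = 143/0.7/70 = 2.92, from the control kit projection in Section III.B: control 2.42, experimental 2.87, ratio 1.19.
- With Poisson counts the ratios are 1.30 and 1.27.
- If experimental invitations come at session 5, the ratio is 1.00.

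**The case against.** The strongest objection is that no sentence closes website counts at the visit. Kit requests, specimen returns and result views arise on the website or at the laboratory, and access has no stated end. With one cut-off on a common clock, the visit gap does no harm. This stands, and it makes the concern conditional. It does not dispose of it, because the arm-dependent anchor is a stated rule and the plan provides nothing that offsets it.

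Second, a reader might infer that experimental men certainly get 28 extra days to request kits. The documents do not support that. They do not say on which day access opens, and the session table and participant flow that might show it are not in the text available. On the session 5 anchor the extra time is 0 to 28 days.

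Third, a reader might extend the point to peers' kit outcomes under Aim 3. Section V.C.3 gives every network member three months from enrollment in both arms, so those outcomes are largely spared.

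Fourth, the size depends on an unknown request pattern. If requests cluster within the first weeks, the excess is 0.3 to 2 points, small beside a standard error of about 8 points at 70 per arm. That also stands.

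Finally, anchoring on the last session is a defensible way to equalize time after training. This is a reason to leave the surveys where they are. It does not justify leaving the counting window open.

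**Conclusion.** The concern holds in conditional form. The unequal visit timing follows from the text: about 28 days on the likelier anchor, about 58 if the check-in counts as the last session. The absence of a common window or time term is also plain.

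The bias arises only if counts close at each man's visit, which is the natural reading but not an explicit one. It affects Aim 3 Index outcomes and the Aim 2 peer count. Under the stated assumptions, a 40% control uptake would be matched by 40.3% to 48.7% in the experimental arm with no training effect. The top figure is an upper bound for the 28-day gap, provided the request rate does not rise over time. The excess is zero if experimental access starts at session 5 or a common cut-off is used. Control uptake, request pattern, count dispersion and access day are assumptions, since the documents give none of them.

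A reader might conclude that the plan will produce a spurious effect. The documents do not support that. They show that it could, and that the plan does not prevent it.

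**What to change.** State in Section V.C.4 that, in both arms, Aim 2 peers recruited and Aim 3 Index website outcomes are counted from randomization to one fixed day, using website dates. Include every randomized Index man and keep zeros. The day should cover training plus three months. Day 120 does so (28 + 91 = 119), plus any planned gap between randomization and session 1. If the check-in is the intended last session, the equivalent is about day 150 (28 + 30 + 91 = 149). Survey visits stay as scheduled.

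The cost is a sentence or two in the plan and a fixed cut-off in the website extract. Network consent times (V.B.1.i) and kit mailing dates (V.C.1) are already recorded there. Control men's access must stay open for about 29 days after their survey falls due (120 − 91).

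The downside is that experimental men have about 92 post-training days in that window (120 − 28). The estimate is then of the whole assigned programme and may be smaller. For example, suppose training multiplied recruiting by 265/143 = 1.85, the ratio of projected kits in Section III.B, but only after session 5, with invitations from session 1. The 120-day ratio before the cap would be (28 + 92 × 1.853)/120 = 1.65.
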